7.3 Subject Population(s) for Analysis

All subjects that received at least one dose of study drug will be evaluated.

8 Safety and Adverse Events

8.1 Definitions

Unanticipated Problems Involving Risk to Subjects or Others (UPIRTSO)

Any unanticipated problem or adverse event that meets the following three criteria:

- Serious: Serious problems or events that results in significant harm, (which may be physical, psychological, financial, social, economic, or legal) or increased risk for the subject or others (including individuals who are not research subjects). These include: (1) death; (2) life threatening adverse experience; (3) hospitalization - inpatient, new, or prolonged; (4) disability/incapacity - persistent or significant; (5) breach of confidentiality and (6) other problems, events, or new information (i.e. publications, DSMB reports, interim findings, product labeling change) that in the opinion of the local investigator may adversely affect the rights, safety, or welfare of the subjects or others, or substantially compromise the research data, **AND**
- Unanticipated: (i.e. unexpected) problems or events are those that are not already described as potential risks in the protocol, consent document, not listed in the Investigator's Brochure, or not part of an underlying disease. A problem or event is "unanticipated" when it was unforeseeable at the time of its occurrence. A problem or event is "unanticipated" when it occurs at an increased frequency or at an increased severity than expected, **AND**
- Related: A problem or event is "related" if it is possibly related to the research procedures.

Adverse Event

An untoward or undesirable experience associated with the use of a medical product (i.e. drug, device, biologic) in a patient or research subject.

Serious Adverse Event

Adverse events are classified as serious or non-serious. Serious problems/events include;

- death
- life threatening adverse experience
- hospitalization
- inpatient, new, or prolonged; disability/incapacity
- persistent or significant disability or incapacity

and/or per protocol may be problems/events that in the opinion of the investigator may have adversely affected the rights, safety, or welfare of the subjects or others, or substantially compromised the research data.

All adverse events that do not meet any of the criteria for serious, will be regarded as **non-serious adverse events**.

Adverse Event Reporting Period

For this study, the study treatment follow-up period is defined as 12 weeks following the last administration of study treatment.

Preexisting Condition

A preexisting condition is one that is present at the start of the study. A preexisting condition will be recorded as an adverse event if the frequency, intensity, or the character of the condition worsens during the study period.

General Physical Examination Findings

At screening, any clinically significant abnormality will be recorded as a preexisting condition. At the end of the study, any new clinically significant findings/abnormalities that meet the definition of an adverse event must also be recorded and documented as an adverse event.

Post-study Adverse Event

All unresolved adverse events will be followed by the investigator until the events are resolved, the subject is lost to follow-up, or the adverse event is otherwise explained. At the last scheduled visit, the investigator should instruct each subject to report, to the investigator, any subsequent event(s) that the subject, or the subject's personal physician, believes might reasonably be related to participation in this study.

Abnormal Laboratory Values

Determination of whether worsening of liver biochemical tests is due to the alcohol-related hepatitis or study drug induced liver injury (DILI) is difficult. An AST or ALT increase >500 IU/L would be considered an indication that the patient might have DILI since AST and ALT are typically $< 300-400$ U/L in AH. Such an increase of > 500 IU/L would trigger prompt evaluation and consideration of discontinuation of the study drug. Considering how difficult it is to distinguish potential DILI from worsening of the underlying liver disease, we have incorporated an external adjudication of all suspected DILI events. An increase in MELD-Na score >5 points from baseline, or doubling bilirubin (2 times the baseline level at enrollment) would warrant urgent review by the DSMB.

The study will be **stopped** if three or more patients develop AST or ALT > 500 U/L or as or as determined by the DSMB.

Hospitalization, Prolonged Hospitalization or Surgery

Any adverse event that results in hospitalization or prolonged hospitalization will be documented and reported as a serious adverse event unless specifically instructed otherwise in this protocol. Any condition responsible for surgery will be documented as an adverse event if the condition meets the criteria for an adverse event.

Neither the condition, hospitalization, prolonged hospitalization, nor surgery are reported as an adverse event in the following circumstances:

- Hospitalization or prolonged hospitalization for diagnostic or elective surgical procedures for a preexisting condition. Surgery will **not** be reported as an outcome of an adverse event if the purpose of the surgery was elective or diagnostic and the outcome was uneventful.

- Hospitalization or prolonged hospitalization for therapy of the target disease of the study, unless it is a worsening or increase in frequency of hospital admissions as judged by the clinical investigator.

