*** Relationship Index**

The relationship of an AE to the Investigational Drug is a clinical decision by the principal investigator (PI) based on all available information at the time of the completion of the CRF and is graded as follows:

1. Not related: a reaction for which sufficient information exists to indicate that the etiology is unrelated to the study drug; the subject did not receive the study medication or the temporal sequence of the AE onset relative to administration of the study medication is not reasonable or the event is clearly related to other factors such as the subject's clinical state, therapeutic intervention or concomitant therapy.
2. Unlikely: a clinical event, including laboratory test abnormality, with a temporal relationship to drug administration which makes a causal relationship improbable and in which other drugs, chemicals, or underlying disease provide plausible explanations.
3. Possible: a clinical event, including laboratory test abnormality, with a reasonable time sequence to administration of the drug but which could also be explained by concurrent disease or other drugs or chemicals; information on drug withdrawals may be lacking are unclear.
4. Probable: a clinical event including laboratory test abnormality, with a reasonable time sequence to administration of the drug, unlikely to be attributed to concurrent disease or other drugs or chemicals and which follows a clinically reasonable response on withdrawal (de-challenge): re-challenge information is not required to fulfill this definition.
5. Definite: a reaction that follows a reasonable temporal sequence from administration of the drug, or in which the drug level has been established in body fluids or tissues, that follows a known or expected response pattern to the suspected drug, and that is confirmed by improvement on stopping or reducing the dosage of the drug, and reappearance of the reaction on repeated exposure (re-challenge).

Severity Index

The maximum intensity of an AE during a day will be graded according to the definitions below and recorded in details as indicated on the CRF. If the intensity of an AE changes over a number of days, then separate entries should be made having distinct onset dates.

1. Mild: AEs are usually transient, requiring no special treatment, and do not interfere with patient's daily activities.

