8.5 Stopping Rules

The study will stop for an individual patient if any of the following occur:

1. The participant decides to withdraw from the study.
2. The participant experiences a Serious Adverse Event (SAE) that, in the opinion of the investigator, is possibly, probably or definitely related to the study drug utilizing the National Cancer Institute's CTCAE system as a guide.
3. The participant experiences a UPIRTSO AND, in the opinion of the investigator and study adjudicator, is related to the study drug
4. The participant experiences a grade 3 or higher CTCAE develop that are determined to be possibly or likely attributable to study drug
5. The participant experiences a medical condition that, in the opinion of the investigator, continuation on the study drug would be detrimental.
6. Decision by the DSMB. If a participant experiences a MELD-Na score increase by more than 5 points from baseline or doubling bilirubin level from enrollment, the DSMB will review the records to determine whether DILI is suspected or changes are attributed to natural course of disease
7. The participant experiences an increase of AST or ALT >500 U/L

Determination of whether worsening of liver biochemical tests is due to the alcoholic hepatitis or study drug induced liver injury (DILI) is difficult. An AST or ALT increase >500 IU/L would be considered an indication that the patient might have DILI since AST and ALT are typically < 300-400 U/L in AH. Such an increase of > 500 IU/L would trigger prompt evaluation and consideration of discontinuation of the study drug. Considering how difficult it is to distinguish potential DILI from worsening of the underlying liver disease, we have incorporated an external adjudication of all suspected DILI events. An increase in MELD-Na score >5 points from baseline, or doubling bilirubin (2 times the baseline level at enrollment) would warrant urgent review by the DSMB.

The study will be put on hold for review with the DSMB if one patient experiences a serious adverse event. The study will be restarted if the DSMB considers the serious adverse events to be unrelated to study drug.

The study will stop overall if any of the following occur:

1. The participant experiences a Serious Adverse Event (SAE) that, in the opinion of the investigator, is possibly, probably or definitely related to the study drug utilizing the National Cancer Institute's CTCAE system as a guide.

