2. Two or more patients have an adverse event grade 3 or above on the CTCAE scale that is determined to be possibly or likely attributable to study drug as per the study adjudicator.
3. Three or more patients develop AST or ALT > 500 U/L.
4. If recommended by the DSMB.

In the event of a SAE, the site will report this to the Mayo Clinic study team. If the SAE is attributable to study drug, the Mayo Clinic study team will report the event to the Institutional Review Board.

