8.6 Medical Monitoring

It is the responsibility of the Principal Investigator to oversee the safety of the study at his/her site. This safety monitoring will include careful assessment and appropriate reporting of adverse events as noted above, as well as the construction and implementation of a site data and safety-monitoring plan (see section 10 “Study Monitoring, Auditing, and Inspecting”). Medical monitoring will include a regular assessment of the number and type of serious adverse events.

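### The target-disease exception in section 8.1 lets some admissions leave adverse event reporting before their relation to acamprosate is graded

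*Combined protocol and SAP*

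**What the plan says.** Section 8.1 of the combined protocol and SAP makes an adverse event that leads to or prolongs hospitalization an SAE, unless the protocol instructs otherwise. It then lists exceptions under this lead-in: "Neither the condition, hospitalization, prolonged hospitalization, nor surgery are reported as an adverse event in the following circumstances". The second exception covers an admission or prolonged stay whose purpose is to treat "the target disease of the study, unless it is a worsening or increase in frequency of hospital admissions as judged by the clinical investigator". Sections 5.7 and 5.8 state that the study is not blinded.

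Four other parts of the plan bear on this:

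- **Preexisting conditions (8.1).** Such a condition "will be recorded as an adverse event if the frequency, intensity, or the character of the condition worsens" during the study.
- **Relationship Index (8.3.1).** Each adverse event is graded from Not related to Definite. Possible includes an event with a reasonable time sequence that "could also be explained by concurrent disease or other drugs or chemicals".
- **Stopping rules (8.5).** "The study will be put on hold for review with the DSMB if one patient experiences a serious adverse event", and "The study will be restarted if the DSMB considers the serious adverse events to be unrelated to study drug". One SAE graded possibly related or higher stops the whole study. So does the following, if judged possibly or likely attributable to the drug: "Two or more patients have an adverse event grade 3 or above on the CTCAE scale".
- **Monitoring (8.6).** "Medical monitoring will include a regular assessment of the number and type of serious adverse events".

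**The concern.** Section 3.4 measures the primary endpoint by adverse event reporting. Section 1.1 names hepatic encephalopathy as the harm that acamprosate might cause, and encephalopathy is also a complication of the enrolled disease. A rule that sets an admission aside as disease, before anyone grades whether the drug contributed, settles part of the trial's question by classification. The judgement belongs to one unblinded investigator, and the text provides no independent review of it. Suspected drug-induced liver injury, where the plan admits the same difficulty, does get external adjudication.

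At stake are the completeness of the adverse event table, the SAE hold and stop rules, and the step from the first five patients (MELD-Na below 20) to the next five (20 or more). Section 1.1 makes that step conditional on no safety concern being identified.

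**Working it through.** The plan has no figure to reproduce: section 7.1 says that no power analysis was done. The check is mainly a reading of the text.

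**1. Order of steps.** Section 8.3 has the worksheet, which carries the relationship field, completed once an adverse event has been identified. The Relationship Index is likewise defined for an adverse event. The exception in 8.1 says that neither the stay nor the condition is one. An excepted admission therefore never reaches grading. No sentence states this order; it follows from the two sections together.

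**2. What stays reportable.** The exception does not apply to an admission that the investigator judges a worsening or an increase in frequency, and the preexisting-condition rule points the same way. Baseline MELD-Na, Child-Pugh, West Haven grade and MMSE give the worsening judgement something to work from. Most decompensation admissions should therefore remain SAEs.

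**3. What can drop out.** Three kinds of admission remain: a recurrent encephalopathy no more frequent than before, a relapse or detoxification admission, and a prolonged index stay judged usual course. The last is realistic because section 3 recruits during hospitalizations.

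**4. What an excepted admission misses.** It is neither an adverse event nor an SAE. It does not trigger the one-SAE hold or the single-SAE stop, does not count toward the grade 3 rule, and is not in the SAE count of 8.6.

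**5. Illustrative size.** Let p be the chance that a patient has a target-disease admission and f the share of such admissions excepted. Neither is in the documents; both are assumed. Assume also independent patients, at most one admission each, and no other SAEs.

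- Chance of a hold in a cohort of five: 1 − (1 − p(1 − f))^5
- Chance that at least one admission is lost among ten: 1 − (1 − pf)^10

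Example with p = 0.20 and f = 0.25. With no exception, the hold chance is 1 − 0.80^5 = 67.2%. With it, 1 − 0.85^5 = 55.6%, a fall of 11.6 points. At least one lost among ten: 1 − 0.95^10 = 40.1%.

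| p | Hold in five, f = 0 | f = 0.10 (fall, points) | f = 0.25 (fall, points) | One or more lost in ten, f = 0.10 | f = 0.25 |
|---|---|---|---|---|---|
| 10% | 41.0% | 37.6% (3.4) | 32.3% (8.7) | 9.6% | 22.4% |
| 20% | 67.2% | 62.9% (4.3) | 55.6% (11.6) | 18.3% | 40.1% |
| 30% | 83.2% | 79.3% (3.9) | 72.0% (11.2) | 26.3% | 54.1% |
| 40% | 92.2% | 89.3% (3.0) | 83.2% (9.0) | 33.5% | 65.1% |

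Falls were taken before rounding. For scale, one lost event turns 1/10 (exact 95% interval 0.3-44.5%) into 0/10 (0-30.8%).

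**The case against.** The strongest reply is that the feared harm lies mostly outside the exception. Patients must be able to consent for themselves, and West Haven and MMSE are taken at baseline, so an encephalopathy that needs admission is ordinarily a worsening and stays reportable. That stands. A reader might infer that the exception hides decompensation in general; the text does not support this.

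Second, *target disease* is not defined. If it means AUD, the condition being treated, liver admissions are never excepted and only relapse or detoxification stays are. This also stands: the encephalopathy case needs the broader reading, which the text allows but does not compel. The undefined term, and the lack of an itemised prior-admission count in 3.1 and 6.1, are missing detail. The case report form and DSMB charter are not in the text and may supply it.

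Third, other safeguards need no adverse event label: the laboratory triggers, DSMB discretion, withdrawal for a change in medical status or a drug-related prolongation (4.4.1), and scheduled MMSE, West Haven and clinical history. Nor is the UPIRTSO route closed, as one might infer from its carve-out for underlying disease. Its definition also covers events more frequent or more severe than expected. These safeguards protect individual patients and keep a signal visible, but they do not ensure that the admission is graded or enters the adverse event table.

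Fourth, an admission that is neither a worsening nor more frequent may well be graded Not related or Unlikely. That is fair, but a recorded grade can be reviewed by the DSMB and an unreported event cannot.

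**Conclusion.** The concern holds as a residual gap. On one unblinded investigator's judgement, disease-like admissions can leave a primary endpoint defined by adverse event reporting, without a recorded causality grade. The conclusion rests on the order of steps inferred from 8.1, 8.3 and the Relationship Index and, for encephalopathy, on the broader reading of *target disease*.

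The size is unknown. The table shows only that, in ten patients, even a small excepted share could matter. It is not an estimate, and a reader should not take 9.6-65.1% as the chance that an event will be lost. A reader might also conclude that every unplanned admission must become an SAE with an automatic hold. The documents do not require that: in patients this ill it could halt the study repeatedly for ordinary disease course, and the endpoint is repaired by recording and grading alone.

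**What to change.** Limit the second exception in 8.1 to admissions planned before the first dose, such as a scheduled procedure or elective detoxification. Record every other admission or prolongation, grade it on the existing Relationship Index, and tabulate it in the safety results and in the count given to the DSMB.

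Admissions that 8.1 already makes SAEs stay SAEs. An admission that the present bullet would have excepted is treated as an SAE under 8.5 if graded Possible or higher. If graded Not related or Unlikely, it is listed as a disease-related admission without an automatic hold. Reporting then no longer turns on a frequency judgement or on what *target disease* means.

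The text change is small: one bullet in 8.1 and a sentence in each of 7.2 and 8.5. The running cost is some extra recording and DSMB listing. The real downside is an occasional hold, or a stop under the single-SAE rule, for an admission graded Possible. Under the assumptions above, the rise in hold probability per five patients is at most the falls in the table (3.0-11.6 points), because only admissions graded Possible or higher would count.

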8.2 Recording of Adverse Events

At each contact with the subject, the study team must seek information on adverse events by specific questioning and, as appropriate, by examination. Information on all adverse events should be recorded immediately in the source document, and also in the appropriate adverse event section of the case report form (CRF). All clearly related signs, symptoms, and abnormal diagnostic, laboratory or procedure results should be recorded in the source document.

All adverse events occurring during the study period will be recorded. The clinical course of each event should be followed until resolution, stabilization, or until it has been ultimately determined that the study treatment or participation is not the probable cause. Serious adverse events that are still ongoing at the end of the study period will be followed up to determine the final outcome. Any serious adverse event that occurs during the Adverse Event Reporting Period and is considered to be at least possibly related to the study treatment or study participation will be recorded and reported immediately.

Adverse events will be classified per the CTCAE Version 5.0, November 27, 2017.

8.3 Reporting of Serious Adverse Events and Unanticipated Problems

When an adverse event has been identified, the study team will take appropriate action necessary to protect the study participant and then complete the Study Adverse Event Worksheet and log. The investigator will evaluate the event and determine the necessary follow-up and reporting required.

8.3.1 Investigator reporting: notifying the Mayo IRB

The investigator will report to the Mayo IRB any UPIRTSOs and NonUPIRTSOs according to the Mayo IRB Policy and Procedures.

Information collected on the adverse event worksheet (*and entered in the research database*):

- Subject's name:
- Medical record number:
- Disease/histology (if applicable):
- The date the adverse event occurred:
- Description of the adverse event:
- Relationship of the adverse event to the research drug:
- If the adverse event was expected:
- The severity of the adverse event: (use a table to define severity scale 1-5**)
- If any intervention was necessary:
- Resolution: (was the incident resolved spontaneously, or after discontinuing treatment)
- Date of Resolution:

The investigator will review all adverse event reports to determine if specific reports need to be made to the IRB. The investigator will sign and date the adverse event report when it is reviewed. For this protocol, only directly related SAEs/UPIRTSOs will be reported to the IRB.

*** Relationship Index**

The relationship of an AE to the Investigational Drug is a clinical decision by the principal investigator (PI) based on all available information at the time of the completion of the CRF and is graded as follows:

1. Not related: a reaction for which sufficient information exists to indicate that the etiology is unrelated to the study drug; the subject did not receive the study medication or the temporal sequence of the AE onset relative to administration of the study medication is not reasonable or the event is clearly related to other factors such as the subject's clinical state, therapeutic intervention or concomitant therapy.
2. Unlikely: a clinical event, including laboratory test abnormality, with a temporal relationship to drug administration which makes a causal relationship improbable and in which other drugs, chemicals, or underlying disease provide plausible explanations.
3. Possible: a clinical event, including laboratory test abnormality, with a reasonable time sequence to administration of the drug but which could also be explained by concurrent disease or other drugs or chemicals; information on drug withdrawals may be lacking are unclear.
4. Probable: a clinical event including laboratory test abnormality, with a reasonable time sequence to administration of the drug, unlikely to be attributed to concurrent disease or other drugs or chemicals and which follows a clinically reasonable response on withdrawal (de-challenge): re-challenge information is not required to fulfill this definition.
5. Definite: a reaction that follows a reasonable temporal sequence from administration of the drug, or in which the drug level has been established in body fluids or tissues, that follows a known or expected response pattern to the suspected drug, and that is confirmed by improvement on stopping or reducing the dosage of the drug, and reappearance of the reaction on repeated exposure (re-challenge).

Severity Index

The maximum intensity of an AE during a day will be graded according to the definitions below and recorded in details as indicated on the CRF. If the intensity of an AE changes over a number of days, then separate entries should be made having distinct onset dates.

1. Mild: AEs are usually transient, requiring no special treatment, and do not interfere with patient's daily activities.
2. Moderate: AEs typically introduce a low level of inconvenience or concern to the patient and may interfere with daily activities, but are usually ameliorated by simple therapeutic measures.

3. Severe: AEs interrupt a patient's usual daily activity and traditionally require systemic drug therapy or other treatment.

